5.2.2 Exclusion Criteria

Subjects must not meet any of the following exclusion criteria:

1. In subjects with a prior null or partial response to pegIFN/RBV treatment at any time prior to pre-screening for this study or any prior failure with pegIFN/RBV plus telaprevir, the presence of variants relative to the appropriate prototypic reference sequence (H77 for 1a or Con1 for 1b) at any of the following positions: NS3 155, 156, or 168; or NS5A 28, 29, 30, 31, 32, 58, or 93.
2. Prior use of an investigational HCV therapy or approved DAA not included in this protocol or the previous AbbVie/Abbott DAA combination study.
3. Females who are pregnant or plan to become pregnant, or breastfeeding, or males whose partners are pregnant or planning to become pregnant within 7 months (or as per local RBV label) after their last dose of RBV.
4. Positive result of a urine drug screen at the Screening Visit for opiates, barbiturates, amphetamines, cocaine, benzodiazepines, phencyclidine, and propoxyphene with the exception of a positive result (including methadone), associated with documented short-term use or chronic stable use of a prescribed medication in that class.

5. Positive test for hepatitis B surface antigen (HBsAg) or anti-HIV antibodies (anti-HIV Ab).
6. Use of known strong inducers (e.g., phenobarbital, rifampin, carbamazepine, St. John's Wort) of CYP3A within 2 weeks prior to study drug administration.
7. Use of any medications listed in [Table 4](#) within 2 weeks or 10 half-lives, of the medication, whichever is longer, prior to study drug administration, including but not limited to:

Table 4. Medications Contraindicated for Use with the Study Drug Regimen

| | | |
|---------------|---|--|
| Alfuzosin | Ergot derivatives (ergotamine, dihydroergotamine, ergonovine, methylethergometrine) | Rifampin |
| Astemizole | Fusidic Acid | Salmeterol |
| Carbamazepine | Lovastatin | Sildenafil* |
| Cisapride | Midazolam (oral) | Simvastatin |
| Efavirenz | Phenobarbital | St. John's Wort |
| | Phenytoin | Terfenadine |
| | Pimozide | Triazolam |
| | | Estrogen-containing medications for systemic use |

* When used for the treatment of pulmonary arterial hypertension.

Not all medications contraindicated with ritonavir, ribavirin and pegIFN are listed in [Table 4](#). Refer to the most current product labeling for each drug for a complete list.

8. Discontinuation of antiviral therapy due to intolerance or a DAA- or RBV-associated adverse event in the previous AbbVie/Abbott DAA combination study (excluding intolerance or AEs associated with telaprevir).
9. Beck's Depression Inventory-II (BDI-II) score of > 21 at Screening. Subjects with BDI-II score > 21 will not be allowed to rescreen.
10. Clinically significant abnormal ECG, ECG with QT interval corrected for heart rate using Fridericia's correction formula (QTcF) > 470 msec at Screening or TI Day 1 visits.

11. Screening laboratory analyses show any of the following abnormal laboratory results:
- Alanine aminotransferase (ALT) $> 7 \times$ upper limit of normal (ULN);
 - Aspartate aminotransferase (AST) $> 7 \times$ ULN;
 - Calculated creatinine clearance (using Cockcroft-Gault method) < 60 mL/min;
 - Albumin $< LLN$;
 - International normalized ratio (INR) > 1.7 ; (Subjects with a known inherited blood disorder and INR > 1.7 may be enrolled with permission of the AbbVie Study Designated Physician.)
 - Hemoglobin $< LLN$;
 - Platelets $< 90,000$ cells per mm^3 ;
 - Absolute neutrophil count $< 1,500$ cells/ μL (< 1200 cells/ μL for subjects of black/African descent);
 - Indirect bilirubin $> 1.5 \times$ ULN and direct bilirubin $> ULN$;
 - Thyroid stimulating hormone (TSH) values outside the normal range.
12. The use of colony stimulating factors, such as granulocyte colony stimulating factor (GCSF) or erythropoietin within 2 months of the Screening Period.
13. Recent (within 6 months prior to study drug administration) history of drug or alcohol abuse that, in the opinion of the investigator, could preclude adherence to the protocol.
14. Clinically significant abnormalities, other than HCV infection, based upon the results of a medical history, physical examination, vital signs, laboratory profile and a 12-lead electrocardiogram (ECG) that make the subject an unsuitable candidate for this study in the opinion of the investigator.
15. Evidence of infection with other HCV genotypes other than genotype 1 at the Screening Visit.

16. Current enrollment in another clinical study or previous enrollment in this study. Concurrent participation in a non-interventional, epidemiologic or registry trials may be permitted with approval by the AbbVie Study Designated Physician.
17. History of solid organ transplantation.

In addition to Exclusion criteria 1 through 18, subjects with compensated cirrhosis must not meet the following criteria:

18. Any current or past clinical evidence of Child-Pugh B or C Classification or clinical history of liver decompensation such as ascites (noted on physical exam), variceal bleeding or hepatic encephalopathy.
19. Serum Alpha-Fetoprotein (sAFP) > 100 ng/mL at Screening.
20. A screening ultrasound suspicious for hepatocellular carcinoma (HCC) and confirmed with a subsequent CT scan or MRI during the screening period.

Rationale for Exclusion Criteria

(1) To exclude subjects with a high likelihood of virologic failure.

(2 – 5, 10 – 12, 14, 15) To ensure safety of the subjects throughout the study.

(6 – 9, 13) To avoid medication interactions which could complicate evaluation of efficacy and safety.

(16 – 21) To select the appropriate subject population.

5.2.3 Prior and Concomitant Therapy

Any medication or vaccine (including over-the-counter or prescription medicines, vitamins and/or herbal supplements) that the subject is receiving at the time of enrollment, or receives during the time periods defined below, must be recorded along with the reason for use, date(s) of administration including start and end dates, and dosage information

including dose, route and frequency. The investigator should review all concomitant medications for any potential interactions. The investigator should confirm that concomitant medication can be safely administered with DAAs as well as ritonavir, pegIFN and RBV. Some medications may require dose adjustments due to potential for drug-drug interactions. Subjects should be on a stable dose of concomitant medications for at least 2 weeks prior to initiation of study drug.

Use of all medications at the time of enrollment and through 30 days after the last dose of DAAs in Substudy 1 will be recorded in the electronic case report form (eCRF). During Substudy 2 and Substudy 3, only antiviral therapies related to the treatment of HCV and medications prescribed in association with a serious adverse event (SAE) will be recorded in the eCRF.

During Substudy 3, investigators should reassess concomitant medications and subjects may resume previously prohibited medications, or revert to pre-study doses, 2 weeks following discontinuation of DAAs, if applicable.

The AbbVie Study Designated Physician should be contacted if there are any questions regarding concomitant or prior therapy(ies).

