5.1.3 Treatment Period (Substudy 1 and Substudy 2)

Substudy 1 – Treatment Intensification (TI) Period

There is one treatment group for this study. After meeting entry criteria, subjects will receive ABT-450/r 200/100 mg, ABT-267 25 mg, pegIFN and RBV. ABT-450/r and ABT-267 will be administered once daily; pegIFN will be dosed once weekly and RBV will be dosed twice daily. See Section 5.5.1 for details.

At the TI Day 1 Visit, subjects will undergo the study procedures identified in [Table 5](#) (and [Table 6](#) for cirrhotic subjects).

Subjects will be administered study drugs at the site on TI Day 1. Plasma and serum samples for pharmacokinetic analysis will be collected at TI Week 1 through TI Week 24 (Substudy 1). All subjects will continue to return to the site on an outpatient basis through TI Week 24 for the study procedures identified in [Table 5](#) (and [Table 6](#) for cirrhotic subjects). Sites should ensure that subjects adhere to the study visits listed in [Table 5](#) (and [Table 6](#) for cirrhotic subjects). Subjects who cannot complete their study visit per the visit schedule through TI Week 24 should ensure they do not run out of study drug prior to their next study visit. Compliance is critical to ensure adequate drug exposure. Some of the Treatment Period study visits and visit activities (including but not limited to vital signs, clinical laboratory tests and concomitant medication assessment) may be conducted in the home or non-hospital/clinic environment by qualified individuals at the request of the investigator and with the agreement of the subject.

Subjects who prematurely discontinue from the DAA study drug treatment in Substudy 1 should return for a TI Week 24/TI Discontinuation Visit and undergo study procedures as defined in [Table 5](#) (and [Table 6](#) for cirrhotic subjects) and as described in Section 5.4.1. The subject should either proceed to Substudy 2 if the investigator feels it is appropriate or proceed to Substudy 3 if it is not appropriate to continue on Substudy 2. Refer to [Figure 3](#), Subject Flow Chart.

Substudy 2 – PegIFN/RBV (PR) Treatment Period

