Subjects who complete TI treatment will continue on to Substudy 2, the PR Treatment Period, for continued dosing of pegIFN and RBV. Subjects who prematurely discontinue TI treatment may also continue on to Substudy 2, unless the investigator feels it is not appropriate to continue pegIFN and RBV either due to toxicity or to lack of virologic response. Substudy 2 will begin the day after the last dose of DAA. Substudy 2 is designed to allow completion of pegIFN + RBV treatment for a total duration of 48 weeks across Substudies 1 and 2 and to monitor HCV RNA levels and emergence of any ABT-450 and ABT-267 resistance-associated variants.

For subjects who complete Substudy 1, an additional 24 weeks of pegIFN and RBV will be administered in Substudy 2. Subjects who complete 24 weeks of treatment in Substudy 2 should undergo the procedures listed in the PR Final/PR Discontinuation Visit in [Table 5](#) (and [Table 6](#) for cirrhotic subjects), not the PR Week 24 visit and then continue on to Substudy 3.

Subjects who receive less than 24 weeks of TI treatment in Substudy 1 may receive pegIFN and RBV in Substudy 2 at the discretion of the investigator, up to a total of 48 weeks across Substudies 1 and 2. All subjects will continue to return to the site on an outpatient basis for the PR Treatment study procedures identified in [Table 5](#) (and [Table 6](#) for cirrhotic subjects). For those subjects who do not complete 24 weeks of TI treatment in Substudy 1, additional study visits as indicated in [Table 5](#) (and [Table 6](#) for cirrhotic subjects) should be performed if required to complete a total of 48 weeks across Substudies 1 and 2. These additional visits are PR Week 24, PR Week 36 and PR

Final/PR Discontinuation Visit (which may be out to 48 weeks or earlier). All subjects should complete the PR Final/PR Discontinuation Visit procedures at that subject's final visit in Substudy 2. In some cases this final visit may fall in between study visits listed in [Table 5](#). Sites should ensure that subjects adhere to the study visits listed in [Table 5](#) (and [Table 6](#) for cirrhotic subjects). Subjects who cannot complete their study visit per the visit schedule should ensure they do not run out of study drug prior to their next study visit. Compliance is critical to ensure adequate drug exposure.

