5.1.4 Post-Treatment Follow-Up Period (Substudy 3)

In Substudy 3, the Post-treatment (PT) Period, subjects will be followed for 48 weeks after the last dose of study drugs for evaluation of the emergence, evolution and persistence of viral resistance to ABT-450/r and ABT-267 and for viral response.

[figure not shown]
All subjects who receive at least 1 dose of DAA will be monitored for viral resistance on an outpatient basis for an additional 48 weeks following the last dose of study drugs, regardless of whether they prematurely discontinue study drug treatment or complete treatment as planned in Substudies 1 and 2. Refer to [Figure 3](#), Subject Flow Chart.

Subjects will return to the study site as outlined in [Table 7](#) (and [Table 8](#) for cirrhotic subjects) for post-treatment visit procedures including resistance monitoring, HCV RNA testing, and assessment of adverse events (for 30 days post-treatment only) and serious adverse events. Substudy 3 will begin the day after the last dose of study drug treatment. Subjects who prematurely discontinue Substudy 3 should return to the site for a PT Week 48/PT Discontinuation Visit as outlined in [Table 7](#) (and [Table 8](#) for cirrhotic subjects).

Some of the Post-Treatment Period study visits and visit activities (including but not limited to vital signs, clinical laboratory tests and concomitant medication assessment) may be conducted in the home or non-hospital/clinic environment at the request of the Investigator and with the agreement of the subject.

All subjects who receive at least one dose of DAA may be offered participation in a separate AbbVie-sponsored observational study to evaluate the durability of virologic response for subjects who achieve SVR or to study the emergence and persistence of resistant variants in subjects who fail treatment.

Figure 3. Subject Flow Chart

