5.2.3.2 Prohibited Therapy

In addition to the medications listed above in [Table 4](#), use of known strong inducers of CYP3A is prohibited within 2 weeks or 10 half-lives, whichever is longer, prior to the initial dose of study through the first 2 weeks after the subject has completed DAA therapy.

Use of any medications contraindicated with pegIFN or RBV is prohibited within 2 weeks prior to the initial dose of study drug through the first 2 weeks after the subject has completed Substudy 2.

Prior to enrollment, subjects should agree to practice two effective methods of birth control while receiving study drugs starting with Study Day 1 and for 7 months after stopping study drug or as directed by the local ribavirin label. Subjects using systemic estrogen-containing contraceptive therapy (including estrogen-containing oral contraceptives) have a higher risk for elevated ALT levels. Subjects using these medications must discontinue them at least 2 weeks prior to study drug administration or 10 half-lives (if known), whichever is longer. Subjects may replace the systemic estrogen-containing contraceptive with a progestin-only hormonal contraceptive method. Estrogen-containing contraceptives may be resumed 2 weeks after the last dose of DAAs.

Refer to the pegIFN, RBV and ritonavir labeling for a list of prohibited medications. HCV medications other than those specified in the protocol will not be allowed during the Treatment Period of the study.

Use of hematopoietic growth factors is not permitted during this study without the approval of the AbbVie Study Designated Physician. Management of hematologic growth factor therapy is the responsibility of the investigator; growth factors will not be provided by the Sponsor, and the Sponsor will not reimburse for the expense of growth factors or their use.

Investigators should refer to the package inserts for erythropoiesis stimulating agents for additional information regarding their use.

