| | PT Wk 2 | PT Wk 4 | PT Wk 8 | PT Wk 12 | PT Wk 24 | PT Wk 36 | PT Wk 48/ PT D/C | |
| Adverse Event Assessment ^a | X | X | X | X | X | X | X | |
| Concomitant Medication Assessment ^b | X | X | X | X | X | X | X | |
| Vital Signs and Weight | X | X | X | X | X | X | X | |
| Pregnancy Test (Females) Urine (u) ^c | X | X | X | X | X | | | |
| Clinical Laboratory Tests | X | X | | | | | X ^d | |
| IP-10 | | | | | X | | X ^d | |
| HCV RNA Sample | X | X | X | X | X | X | X | |
| HCV Resistance Testing | X | X | X | X | X | X | X | |
| Archive Plasma Sample | X | X | | | | | X | |

PT = Post-treatment; Wk = week; D/C = discontinuation

- AEs will be collected for only 30 days following last dose of study drugs. SAE's will be collected during the entire Substudy 3 period.
- Only concomitant medications related to HCV treatment and/or medications prescribed in association with a serious adverse event will be collected during Substudy 3.
- Post-treatment pregnancy testing is to be completed at the visits outlined in Table 7. Additional pregnancy testing (urine and/or serum) during the Post-treatment Period, e.g., at PT Week 16, PT Week 20, PT Week 28 or at other time points should be completed according to the local RBV label and/or local treatment guidelines for RBV or local legal requirements. Additional pregnancy testing (urine and/or serum) done outside of the visits specified in Table 7 should be completed using the unscheduled test kit or the subject can perform the tests at home with test kits provided by the site.
- Sample to be drawn only if conducting a Discontinuation Visit.

Table 8. Additional Study Activities for Cirrhotic Subjects Only – Substudy 3 Post-Treatment

| Activity | Substudy 3 Post-Treatment (PT) Period | | | | | | | |
|--|---------------------------------------|---------|---------|----------|----------|----------|---------------------|--|
| | PT Wk 2 | PT Wk 4 | PT Wk 8 | PT Wk 12 | PT Wk 24 | PT Wk 36 | PT Wk 48/ PT D/C | |
| Clinical Laboratory Tests | X | X | | | X | | X | |
| Child-Pugh Score | | | | X | | | | |
| HCC Screening: Liver Ultrasound and Alpha Fetoprotein ^a | | | | | X | | X | |

a. If additional liver ultrasound testing is required it should be completed as an unscheduled visit. An ultrasound result suspicious for HCC will be confirmed with CT scan or MRI

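### Protocol 5.2.3 times the restart of prohibited drugs only from the end of the DAAs; read literally, it frees pegIFN/RBV-contraindicated drugs up to 14 days before 5.2.3.2 does (low impact).

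*Protocol*

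**What the plan says.** Two parts of the Protocol set restart dates.

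- **Section 5.2.3 (general rule).** The sentence opens "During Substudy 3, investigators should reassess concomitant medications" and goes on to say that "subjects may resume previously prohibited medications, or revert to pre-study doses, 2 weeks following discontinuation of DAAs, if applicable". It mentions one clock, the end of the DAAs, names no drug class and does not refer to 5.2.3.2. Elsewhere, 5.2.3 asks the investigator to confirm that concomitant drugs are safe with the DAAs, ritonavir, pegIFN and RBV, and sends questions to the Study Designated Physician.
- **Section 5.2.3.2 (prohibitions).** There are two clocks. Strong CYP3A inducers are barred "through the first 2 weeks after the subject has completed DAA therapy", and estrogen-containing contraceptives are released on the same interval after the DAAs. Drugs contraindicated with pegIFN or RBV are barred "through the first 2 weeks after the subject has completed Substudy 2".

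The period boundaries are in 5.1.3 and 5.1.4: "Substudy 2 will begin the day after the last dose of DAA", and "Substudy 3 will begin the day after the last dose of study drug treatment". A subject who stops the DAAs early may also skip Substudy 2 and "proceed to Substudy 3 if it is not appropriate to continue on Substudy 2".

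On recording, a note to Table 7 in section 5.3.1 says: "Only concomitant medications related to HCV treatment and/or medications prescribed in association with a serious adverse event will be collected during Substudy 3".

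**The concern.** The general rule puts every restart on the DAA clock, while the prohibition section puts one class of drug on the pegIFN/RBV clock. For a subject who completes treatment, the two clocks are 24 weeks apart. By the time Substudy 3 opens, the only waiting time named in 5.2.3 expired long ago. A site following that sentence alone would find nothing to delay a pegIFN/RBV-contraindicated drug, although 5.2.3.2 still bars it for two weeks.

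What is at stake is the two-week tail that the sponsor chose to keep after pegIFN/RBV. The window falls within the 30 days after study drug in which all adverse events are collected (section 6.4). For a completer, a drug restarted in that window would not reach the eCRF unless it was for HCV or tied to a serious adverse event. That limit on recording is a deliberate collection rule and not a product of this wording, but it means an early restart would leave little trace in the data.

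**Working it through.** The plan gives no figure to reproduce, so the check is a day count.

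**Inputs**
- DAAs run for 24 weeks: last dose on day 168 (sections 5.1.3 and 5.5.1).
- A completer then has 24 more weeks of pegIFN/RBV: last day 336 (section 5.1.3).
- Substudy 3 starts the day after the last dose: day 337 for a completer (section 5.1.4).
- Both waiting times are 2 weeks, or 14 days (sections 5.2.3 and 5.2.3.2).

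**Formulas.** Let d be the number of days of pegIFN/RBV after the last DAA dose, and count days from that dose.
- First day allowed by 5.2.3, which needs both Substudy 3 and the post-DAA wait: max(d + 1, 15).
- First day allowed by 5.2.3.2 for pegIFN/RBV-contraindicated drugs: d + 15.
- Gap: d + 15 − max(d + 1, 15) = min(d, 14).

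For d = 0, section 5.2.3.2 gives no explicit end date because Substudy 2 is not entered. I take the end of pegIFN/RBV as the anchor.

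**Completer (d = 168), in study days**
- The post-DAA wait ends on day 168 + 14 = 182, well before Substudy 3.
- 5.2.3 allows restart from day 337 (about week 48).
- 5.2.3.2 prohibits through day 336 + 14 = 350 (week 50) and allows restart from day 351.
- Gap: 351 − 337 = 14 days.

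**Other lengths of Substudy 2, in days after the last DAA dose**

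| d (days) | First day under 5.2.3 | First day under 5.2.3.2 | Gap (days) |
|---|---|---|---|
| 0 | 15 | 15 | 0 |
| 7 | 15 | 22 | 7 |
| 14 | 15 | 29 | 14 |
| 28 | 29 | 43 | 14 |
| 168 | 169 | 183 | 14 |

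**When the gap meets a scheduled visit.** Table 7 places the first Substudy 3 medication assessment at PT Week 2. For a completer, nominal day 14 after treatment is day 336 + 14 = 350, the last prohibited day. A restart inside the window would therefore have to be decided at the PR Final visit, where Table 5 also schedules a medication assessment, or between visits.

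**Recording.** Section 5.2.3 records all medications through 30 days after the last DAA dose. For a completer that is day 168 + 30 = 198, long before the window. With a short Substudy 2, the window ends d + 14 days after the last DAA dose, so it lies wholly within the 30 days when d ≤ 16, and a restart might then be captured.

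**After the fix.** Both sections give day 351 for a completer, and the gap is 0.

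**The case against.** The strongest reply is that the sections can be read together. The 5.2.3 sentence is permissive, carries a qualifier about applicability and is tied to stopping the DAAs. Its natural subject is drugs barred because of the DAAs, and 5.2.3.2 uses the same post-DAA interval for those. An express prohibition in the dedicated subsection would normally prevail over a general permission. The sentence also pairs restart with the investigator's reassessment, and the scheduled reassessment comes as the prohibition ends. The contraindication lists are left to product labeling, so the documents do not show that any of the up to 35 subjects would take such a drug.

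Most of this stands, and it is why the impact is low. It does not remove the inconsistency. The qualifier neither says which drugs are excluded nor supplies a second date, and nothing in the text states that 5.2.3.2 takes precedence. The duty to confirm safety with pegIFN and RBV concerns giving drugs together, so it does not clearly enforce a waiting time after dosing has stopped.

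A reader might infer three stronger things, none of which the documents support:
- *That 5.2.3 allows these drugs from week 26, while pegIFN/RBV is still being given.* The permission is placed in Substudy 3, so it cannot start before about week 48 for a completer.
- *That 5.2.3 expressly releases every prohibited drug and overrides 5.2.3.2.* The sentence does not say so; the conflict arises only on a literal reading of an undifferentiated phrase.
- *That 5.2.3 forces DAA-adjusted doses to stay changed until Substudy 3.* No sentence forbids earlier reversion. Section 5.2.3.2 releases estrogen-containing contraceptives two weeks after the DAAs, which for a completer is during Substudy 2, and 6.7.5 calls for doses to be readjusted when creatinine clearance improves. This is at most an ambiguity.

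**Conclusion.** The inconsistency is real and small. On a literal reading, 5.2.3 releases pegIFN/RBV-contraindicated drugs min(d, 14) days before 5.2.3.2 does: 14 days for anyone with at least 14 days of Substudy 2, including every completer, and none if all drugs stop together. Fourteen days is the maximum that the text allows, not an expected exposure. Those affected are at most a subset of the up to 35 planned subjects, and the number could be zero.

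The result assumes dosing on the planned schedule for a completer, Substudy 2 ending with the last dose of study drug, and the end of pegIFN/RBV as the anchor when Substudy 2 is not entered. No particular drug, interaction or harm is shown. SVR12 and its analysis are unaffected. It is worth correcting, at low severity, because a safety instruction gives the wrong date for one class of drug and one sentence puts it right.

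**What to change.** In 5.2.3, keep the investigator's reassessment and limit the two-weeks-after-DAA rule to medications prohibited or dose-adjusted because of the DAAs or ritonavir. Then add a sentence to this effect: *medications contraindicated with pegIFN or RBV may be resumed only 2 weeks after the end of Substudy 2, as stated in 5.2.3.2, or 2 weeks after the end of pegIFN/RBV if Substudy 2 is not entered; a drug in both classes follows the later date.*

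Keep the end of Substudy 2 as the anchor. PegIFN is weekly, and the SAP (section 6.1) counts the end of treatment from the last injection plus 7 days. Where RBV had stopped earlier, a rule counted from the last dose could expire up to 7 days before one that includes the final dosing week. Using the anchor already in 5.2.3.2 avoids creating a second date.

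The change needs no new procedure, data item or analysis. As a protocol change it should go through the usual amendment route with IEC/IRB approval (section 9.1), so it is best included in the next amendment and does not justify one of its own.
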